Secondary aims include assessment of the tolerability of the treatment and evaluation of the effect of the intervention on glycemic control as measured by continuous glucose monitoring for 7 days after each treatment. In addition, the pharmacokinetics of intranasal naloxone will be characterized and the relationship between plasma drug concentration and response will also be explored. In this proof of principle experiment, we will determine if the administration of intranasal naloxone preserves the counterregulatory response to subsequent hypoglycemia. If it does, future investigation will focus on developing this agent for use in the real world, with experiments designed to identify the minimum dose necessary to achieve the preservation, define the duration of the effect, and examine the ease of usability for patients with type 1 diabetes.

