Participants will be instructed to call the investigators if they have symptomatic hypoglycemia with a glucose of <70 mg/dL or asymptomatic hypoglycemia with a glucose of <54 mg/dL during the 6 days before the exercise studies, after discharge on day 1 or before the hypoglycemic clamp is started on day 2. Participants will be rescheduled if they have episodes of hypoglycemia (defined as symptomatic hypoglycemia and a blood glucose or CGM reading <70 mg/dL or asymptomatic hypoglycemia with a blood glucose of < 54 mg/dL) for more than 20 minutes in the days before Day 1 of the study.

Part 1 Day 1: Participants will be instructed to report for the visit in a fasting state. Before any other research procedures take place, participants will be randomized to receive either naloxone or saline. Intravenous catheters will be placed for the subsequent infusion of 1.0 mU/kg/min insulin, potassium phosphate or potassium chloride (120 mEq/l at 40 cc/hr), and 20% dextrose as needed to maintain euglycemia. When participants reach euglycemia (~ 95 mg/dL), they will be instructed to begin exercise on a stationary bicycle. Adjustments in the exercise workload will be made to assure that participants exercise at a workload requiring 60% of their VO₂peak for 45 minutes based on the VO₂ measured every 15 minutes. They will then be given a 5 minute rest break, followed by another 45 minute period of exercise at 60% VO₂peak. At the start of exercise and 45 minutes after the start of the morning exercise period, participants will be given a 4.0 mg doses of intranasal naloxone or saline in the same volume, according to the randomization assignment.

Participants may be asked to allow a download of their personal glucose meter/pump data. This will be done in research offices using secure software specific for the brand of the glucose meter/pump.

At the completion of the morning exercise, participants will be allowed to rest 3 hours and eat a 15g carbohydrate measured snack. Glycemia will be maintained at euglycemia during this rest period.

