At 1 pm, the afternoon period of exercise will start and will be maintained as in the morning for a total of 2 hours. A third dose of 4.0 mg intranasal naloxone or the same volume of saline will be administered at the start of the afternoon exercise, and a final dose of 4.0 mg intranasal naloxone will be given 45 minutes after the start of the afternoon exercise. Blood samples for subsequent measurement of naloxone will be collected at 4-5 predetermined time points from each participant to allow subsequent population pharmacokinetic modeling. After completing the afternoon exercise, participants will be sent home with instruction on avoiding hypoglycemia and using the CGM. Before participants are sent home, a meal will be provided.

Part 1 Day 2: Participants will return the following day, and undergo a two-hour hyperinsulinemic (infusion of 2.0 mU/kg/min) hypoglycemic clamp in which blood glucose will be allowed to drop to 50 mg/dL. Symptom scores will be collected using a standardized questionnaire before and every 15 minutes during the hypoglycemic clamp study. Samples for later measurement of epinephrine, norepinephrine, glucagon and cortisol will be collected at baseline and every 15 minutes during the two-hour infusion period. After completing the clamp, participants will be

PROTOCOL TITLE: Hypoglycemia after exercise in type 1 diabetes: Intranasal naloxone as a novel therapy to preserve hypoglycemia counterregulation

VERSION 8 – December 7, 2018

given a meal and instructions for using the CGM for the next 7 days. At the completion of Part 1, participants will be scheduled to return to complete part two to receive the alternate therapy.

Wash-out Period: For a total of approximately 7 weeks, participants will be instructed to continue with all normal activities.

Seven days before scheduled Part 2 Visit: Participants will be asked to come in for a visit to apply the CGM. Application of the sensor and instructions are as above.

Part 2 Day 1 and Part 2 Day 2: The second part of the study will follow exactly as above with the exception that the participant will receive the alternate therapy to complete the cross-over. Those who received naloxone in Part 1 will receive saline in Part 2, and vice versa.

A mid-point A1C may be collected at this visit. A clinical A1C from the medical record can be used if within three months of the Screening A1C.

5.3 Follow-Up:

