Participants will be contacted at 1 week post final study procedure for adverse event assessment. This can be done by either telephone or email.

PROTOCOL TITLE: Hypoglycemia after exercise in type 1 diabetes: Intranasal naloxone as a novel therapy to preserve hypoglycemia counterregulation

VERSION 8 – December 7, 2018

	Screening	-6 to -1 days Part 1 Day 1	Part 1 Day 1		Part 1 Day 2	+1 to +7 days Part 1 Day 2	7 Week Washout Period	CGM-Only -7 Days before Part 2	-6 to -1 days Part 2 Day 1	Part 2 Day 1		Part 2 Day 2	+1 to +7 days Part 2 Day 2
			AM	PM						AM	PM		
Consent	X												
A1c	X										X		
VO ₂ peak/bike	X												
Education	X												
Urine Pregnancy Test	X		X								X		
Apply CGM	X								X				
Wear CGM		X	X	X	X	X				X	X	X	X
Home blood sugar monitoring		X				X				X			X
Randomization			X										
Download glucose meter/pump			X								X		
Exercise			X	X							X	X	
IV Infusion (insulin, glucose, potassium)			X	X	X						X	X	X
Naloxone/saline			X ¹	X ¹							X ¹	X ¹	
Blood collection: naloxone concentrations (only collected during active study drug)			X ²	X ²							X ²	X ²	
Blood collection: hormones (epinephrine, norepinephrine, glucagon, cortisol)					X ⁶								X ⁶
Glucose measurement			X ⁵	X ⁵	X ⁵						X ⁵	X ⁵	X ⁵
Blood Pressure	X												
Heart Rate			X ³	X ³							X ³	X ³	
VO ₂			X ⁴	X ⁴							X ⁴	X ⁴	
Questionnaires	X				X ⁷								X ⁷
Usual Activities							X						
Snack, if necessary			X	X	X						X	X	X
Meal				X	X						X	X	

¹ Naloxone/saline 4.0mg administered twice, time zero and +30 minutes

² Serum collection for naloxone at time points every 20-40 minutes

³ Heart rate collected continuously

⁴ VO₂ collected every 15 minutes

⁵ Collected from IV, resulted on bedside Analox machine

⁶ Serum collection: hormones

⁷ Questionnaires every 15 minutes

PROTOCOL TITLE: Hypoglycemia after exercise in type 1 diabetes: Intranasal naloxone as a novel therapy to preserve hypoglycemia counterregulation

VERSION 8 – December 7, 2018

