8.0 Study Duration

Expected duration for total participation time is approximately 15 weeks.

- Screening Visit: 1 day
- Glucose Monitoring: 6 days
- Part 1, Day 1 and Day 2: 2 days
- Glucose Monitoring: 7 days
- Wash-out period between Part 1 and Part 2: 7 weeks
- Glucose Monitoring: 6 days
- Part 2, Day 1 and Day 2: 2 days
- Glucose Monitoring: 7 days

It is expected to take approximately two and a half years (Y1, Y2, part of Y3) to enroll enough participants to have 28 individuals in matched-pairs complete both parts of the study.

It is expected to take approximately three years (Y1, Y2, Y3) to complete all study procedures on all participants and all final data analysis.

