16.0 Data Management

16.1 Data Analysis Plan:

All randomized subjects who have complete outcome data for one or both of parts 1 and 2 will be included in the analysis. The Aim 1 primary outcome is difference in symptom scores collected during hypoglycemia on day 2 following the intranasal naloxone vs intranasal saline intervention on day one. The Aim 2 primary outcome will be the peak epinephrine during the hypoglycemic clamp on day 2 of each part, thus each participant will have two observations: one from their naloxone experiment and one from their saline experiment. The statistician will fit a general linear mixed model with fixed effects for treatment (Naloxone vs. saline), treatment order (Naloxone first vs. saline first), and period (Part 1 vs. Part 2) and a random effect for participant. The level of significance will be set at $p < 0.05$.

The study has been confidently designed, with a washout period of 7+ weeks between Parts 1 and 2, to ensure minimization of the possibility of a treatment effect from Part 1 that lingers into Part 2. Summary statistics will be used to examine whether measures of metabolic conditions showed clinically meaningful differences between naltrexone studies and saline studies. If there are, then the treatment comparison will be repeated using the same linear mixed model but with additional

PROTOCOL TITLE: Hypoglycemia after exercise in type 1 diabetes: Intranasal naloxone as a novel therapy to preserve hypoglycemia counterregulation

VERSION 8 – December 7, 2018

adjustment for the metabolic parameters of concern; this will be done separately for epinephrine and symptoms scores.

Secondary outcomes will be analyzed similarly, using models appropriate for the scale of the outcome (e.g., linear models, logistic models, binomial models).

Data analysis will also consider adjustment for important baseline characteristics, such as age and sex. Diagnostics will be examined to assess model assumptions. Baseline characteristics of those who do complete vs. those who do not complete both parts will be examined and used to inform interpretation of the treatment effect.

16.2 Power Analysis:

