18.0 Provisions to Monitor the Data to Ensure the Safety of Participants

18.1 Data Integrity Monitoring.

While there will be no planned interim data analysis, the PI will periodically review data for completeness and to ensure that all procedures are being followed as detailed in the protocol. The assigned Regulatory Specialist or CTSI monitor will also perform periodic quality assurance monitoring at any point requested by the PI or at least annually.

18.2 Data Safety Monitoring.

An unblinded Data and Safety Monitoring Board (DSMB) will be assembled, including the following individuals:

- Independent monitor: endocrinologist with clinical and research experience.
 - [name]. Associate [name] of Pediatric Endocrinology. Department of Pediatrics, University of Minnesota
- Independent monitor: endocrinologist with clinical and research experience.
 - [name]. Associate Professor of Pediatric Endocrinology Department of Surgery, University of Minnesota
- Study monitor: statistician with research experience
 - [name]. Associate [name] of Biostatistics, School of Public Health, University of Minnesota

The DSMB will review any incidence of early stopping of the study and any incidence of an adverse or serious adverse event at time points of post-5, 10, 15 randomizations and at the final randomization. If at any point, during Part 1 or Part 2, the study was stopped early and an adverse or serious adverse event was reported, the DSMB will review that participant's

PROTOCOL TITLE: Hypoglycemia after exercise in type 1 diabetes: Intranasal naloxone as a novel therapy to preserve hypoglycemia counterregulation

VERSION 8 – December 7, 2018

data within two weeks. The DSMB will be informed of all adverse and serious adverse events within 48 hours and other events within 7 days. The DMSB may recommend termination of the study at any time based on safety concerns.

The Principal Investigator will oversee the safety of the study, including careful assessment and appropriate reporting of adverse events. All adverse and serious adverse events will be discussed with the PI within 48 hours for standard assessments (causality, expectedness, severity, and seriousness). IRB and other regulatory reporting requirements will be reviewed by study staff and followed with assistance of the Regulatory Specialist assigned to the study.

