Specific safety data to be monitored includes those associated with naloxone administration and hypoglycemia. Participants will be continuously monitored during the administration of the naloxone/placebo by study personnel. At each study visit following consent, participants will be asked about their health since the last time they were seen by the study staff.

- Those specifically related to naloxone: musculoskeletal pain, headache, nasal symptoms, blood pressure, and other cardiac events.
- Glucose levels: if at any point during Part 1 or Part 2, glucose monitoring becomes impossible because of technical failure or other issue or if the MD/PA present suspects an immediate concern, the study will be immediately halted and blood sugar given to participant.

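### No adverse event contact is scheduled after Part 1: the next solicited enquiry comes 6 to 8 weeks after the clamp, against 1 week after Part 2

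*Combined protocol and SAP*

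**What the plan says.** - **Follow-up (5.3).** "Participants will be contacted at 1 week post final study procedure for adverse event assessment". This may be done by telephone or email. It is the only dedicated adverse event contact in the protocol.
- **Enquiry at visits (18.2).** "At each study visit following consent, participants will be asked about their health since the last time they were seen by the study staff". Participants are also monitored continuously while study treatment is given.
- **Between the parts (5.2 and the schedule).** After the Part 1 clamp, participants go home with a CGM for 7 days. Then comes the washout: "For a total of approximately 7 weeks, participants will be instructed to continue with all normal activities". The next encounter is the CGM application visit, seven days before Part 2. The schedule shows only home monitoring and usual activities in between.
- **Length of the washout.** Section 8.0 has "Wash-out period between Part 1 and Part 2: 7 weeks", listed apart from the glucose monitoring before and after it. Section 16.1 has "with a washout period of 7+ weeks between Parts 1 and 2".
- **Call-in instruction (5.2).** This covers hypoglycemia in the 6 days before the exercise studies and "after discharge on day 1 or before the hypoglycemic clamp is started on day 2". It does not extend past the start of the clamp.
- **Reporting (18.2).** "The DSMB will be informed of all adverse and serious adverse events within 48 hours". Discussion with the principal investigator is also due within 48 hours. Neither rule says when the clock starts.
- **Aim (Section 1.0).** "Secondary aims include assessment of the tolerability of the treatment".

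**The concern.** Both parts involve the same exercise, the same intranasal procedure and the same clamp, but only Part 2 is followed by a planned question about harm. This matters in three ways.

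1. **Detection.** An event in the days after the Part 1 clamp may reach staff only about a week before the participant is exposed again. The DSMB reviews events after 5, 10 and 15 randomizations (18.2). At those points some participants may be in washout and not yet asked about anything after their clamp.
2. **Loss.** Section 13.2 stops data collection when a participant withdraws. Someone who leaves during washout, possibly because of an event, may never be asked.
3. **Comparability.** Tolerability is a secondary aim, but no adverse event window is defined for it. An illness three weeks after Part 1 can be collected. The same illness three weeks after Part 2 falls beyond the last contact.

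**Working it through.** The plan states no figure for this gap, so there is none to reproduce. It follows from calendar arithmetic.

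**Inputs.** Part 1 Day 2 is day 0. Home CGM after the clamp lasts 7 days (5.2). The washout is 7 weeks, or 49 days (5.2, 8.0). Monitoring before Part 2 lasts 6 days (8.0). The CGM visit is 7 days before Part 2 (5.2). The contact after Part 2 is at 7 days (5.3).

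**Formula.** Gap = (day of Part 2 Day 1) − 7.

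| Reading of the 7 weeks | Part 2 Day 1 | Gap to CGM visit | Ratio to 7 days |
|---|---|---|---|
| Whole interval between the parts | day 49 | 49 − 7 = 42 days | 6.0 |
| Follows the 7 CGM days and includes the second lead-in | 7 + 49 + 1 = day 57 | 57 − 7 = 50 days | 7.1 |
| Section 8.0 list taken in sequence | 7 + 49 + 6 + 1 = day 63 | 63 − 7 = 56 days | 8.0 |

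This assumes that the CGM application counts as a study visit at which the health question is asked. If it does not, the next enquiry is Part 2 Day 1, at 49 to 63 days.

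**Does the 48-hour rule fail?** The gap is 42 × 24 = 1,008 to 56 × 24 = 1,344 hours.
- If the clock runs from staff awareness, the rule can still be met once the event is known. The fault is then late detection.
- If it runs from onset, an event first learned of at a 7-day contact (7 × 24 = 168 hours) can also be too late. That applies to Part 2 as it stands, and it would apply to the same contact added after Part 1.

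**Does the unequal window bias naloxone against saline?** The following figures are assumptions for illustration: 0.1 background events per participant-week, no drug effect, 17 participants naloxone-first and 13 saline-first.

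*Raw means, windows of 8 weeks and 1 week (0.8 and 0.1 expected events):*
- Naloxone: (17 × 0.8 + 13 × 0.1)/30 = 14.9/30 = 0.497
- Saline: (13 × 0.8 + 17 × 0.1)/30 = 12.1/30 = 0.403
- Difference: 2.8/30 = 0.093

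*Raw means, windows of 6 weeks and 1 week (0.6 and 0.1):*
- Naloxone: (17 × 0.6 + 13 × 0.1)/30 = 11.5/30 = 0.383
- Saline: (13 × 0.6 + 17 × 0.1)/30 = 9.5/30 = 0.317
- Difference: 2.0/30 = 0.067

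With a 15:15 split the raw difference is 0. If the larger sequence is saline-first, the sign reverses.

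*Adjusted for period (8-week case):* the within-person naloxone-minus-saline difference is 0.8 − 0.1 = +0.7 in the naloxone-first sequence and 0.1 − 0.8 = −0.7 in the saline-first sequence. The treatment effect is the average of the two sequence means, (0.7 − 0.7)/2 = 0, whatever the split.

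**The case against.** The strongest case for the plan is that the gap exposes little.

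- **Dosing harms are covered alike in both parts.** Treatment is given under observation and Day 2 is an enquiry point the next day. This stands. Only events after Day 2 are affected.
- **Later hypoglycemia is recorded prospectively.** CGM and home glucose monitoring run for 7 days after each part, and symptoms counted within glucose ranges are a secondary endpoint (3.2). So the recall and unequal-window points do not apply to that outcome. The plan does not say that staff review these data in real time.
- **There is an enquiry before re-exposure.** The CGM visit is 7 days before Part 2, which leaves time for a 48-hour report. This stands for participants who are still enrolled and who remember the event.
- **Participants may report unprompted, and each event gets a causality assessment (18.2).** Both stand. Nothing in the protocol attributes washout illness to the Part 1 treatment.

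Two stronger readings are tempting, and the documents do not support either.

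1. *The gap defeats the 48-hour rule.* The start of the clock is not stated, so no breach can be shown. On an onset clock the problem is not specific to Part 1, and a 7-day call would not cure it.
2. *The unequal windows bias the treatment comparison.* A spurious difference appears only in a raw comparison with unequal sequences. Section 13.2 makes unequal sequences possible, because replacements are newly randomized. But Section 16.1 includes a period term and says that secondary outcomes are analyzed similarly, and that term takes the illustrative difference to 0. One reservation remains: tolerability is an aim in Section 1.0 but is not listed among the endpoints in 3.2, so its own analysis is not written out. A period term also cannot recover events that were forgotten or never collected.

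**Conclusion.** The gap is real. No solicited enquiry about harm is scheduled for 42 to 56 days after Part 1 Day 2, against 7 days after Part 2. The range comes from the different readings of the washout, and the figure assumes that the CGM visit counts as an enquiry point.

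The consequence is narrower than the gap suggests. It concerns events other than hypoglycemia that occur after the Part 1 clamp, which may be detected late, poorly recalled, or lost through withdrawal. It also leaves post-clamp adverse event windows that differ 6- to 8-fold by period, which adds noise to the tolerability aim. No breach of the reporting rule and no bias in a period-adjusted comparison has been shown. This is a cheap improvement to the plan, and the primary outcomes are not affected.

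**What to change.** - **5.3 and the schedule:** add the same telephone or email adverse event contact 1 week after Part 1 Day 2 as after Part 2 Day 2. The first solicited question after the clamp then comes at day 7 in both parts.
- **16.1:** compare tolerability between treatments on one window in both parts, from Day 1 dosing to 7 days after Day 2, with a period term. List washout events separately.
- **18.2:** state whether the 48-hour clock runs from onset or from staff awareness.

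Cost: one extra contact per participant, about 30 in all, with a small amount of coordinator time and three short text changes. No study procedure or treatment changes.

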6.0 Data and Specimen Banking

6.1 Storage and Access:

Participant's glucose meter/pump data will be downloaded and stored in a de-identified manner on AHC-IS managed servers.

If participants agree, there are two optional parts of this study involving banking. For both the specimen and contact data, only the research study team will have access.

- Blood specimen to be stored indefinitely in secure locked labs. Blood will be stored for future analysis on metabolites to better understand diabetes, hypoglycemia, and basic metabolism. Samples will only be stored with a code and no identifying information.
- Contact information to be stored indefinitely in secure, REDCap™ databases. Information will be used to contact participants about future studies. Data stored will include identifiers, primarily consisting of name, telephone, email, and address.

6.2 Data:

- Glucose meter/pump data will only be stored with a code and no identifying information
- Blood sample will only be stored with a code and no identifying information or other data.
- Future contact stored data will include identifiers, primarily consisting of name, telephone, email, and address for those who indicate they are willing to be contacted in the future.

6.3 Release/Sharing:

No data or specimens will be released or shared.

7.0 Sharing of Results with Participants

Not applicable. Results will not be shared.

8.0 Study Duration

Expected duration for total participation time is approximately 15 weeks.

- Screening Visit: 1 day
- Glucose Monitoring: 6 days
- Part 1, Day 1 and Day 2: 2 days
- Glucose Monitoring: 7 days
- Wash-out period between Part 1 and Part 2: 7 weeks
- Glucose Monitoring: 6 days
- Part 2, Day 1 and Day 2: 2 days
- Glucose Monitoring: 7 days

It is expected to take approximately two and a half years (Y1, Y2, part of Y3) to enroll enough participants to have 28 individuals in matched-pairs complete both parts of the study.

It is expected to take approximately three years (Y1, Y2, Y3) to complete all study procedures on all participants and all final data analysis.

